APPENDIX 2: Sampling Times for Central Laboratory Analysis

Cycle	Week	Pharmacokinetic	Pharmacodynamic	Immuno-globulin	Immuno-genicity	Efficacy	β-2 micro-globulin	Tumour tissue/ CD20 lymphoma cell	Biomarker
Screening	-	-	-	-	-	Any time	Any time	Any time	-
Induction 1	1	Predose, after 1 hour	Predose, after 1 hour	Predose	Predose	-	-	-	Before infusion
Induction 2	2	Predose, after 1 hour	Predose	-	-	-	-	-	-
Induction 3	3	Predose, after 1 hour	Predose	-	-	-	-	-	-
Induction 4	4	Predose, after 1 hour	Predose	-	-	-	-	-	-
EOT 1	5	Anytime during the day	Anytime during the day	Anytime during the day	-	-	-	-	-
Maintenance 1 (EOT 2)	12 (M3)	Predose, after 1 hour (If EOT 2, anytime during the day)	Predose, after 1 hour (If EOT 2, anytime during the day)	Predose (If EOT 2, anytime during the day)	Predose (If EOT 2, anytime during the day)	Radiological assessment (Patient who is PD has to be excluded from the maintenance therapy)	Before infusion (If EOT 2, anytime during the day)	-	-
Maintenance 2	20 (M5)	Predose, after 1 hour	Predose, after 1 hour	Predose	-	-	-	-	-
Maintenance 3	28 (M7)	Predose	Predose	Predose	Predose	Radiological assessment	Before infusion	-	-

Cycle	Week	Pharmacokinetic	Pharmacodynamic	Immunoglobulin	Immunogenicity	Efficacy	β-2 microglobulin	Tumour tissue/ CD20 lymphoma cell	Biomarker
Maintenance 6	52 (M13)	-	-	-	Predose	Radiological assessment	Before infusion	-	-
Maintenance 9	76 (M19)	-	-	-	Predose	Radiological assessment	Before infusion	-	-
EOT 3	108 (M27)	-	-	-	Anytime during the day	Radiological assessment	Anytime during the day	-	-
Follow-Up	-	-	-	-	(First follow-up visit)	Every 6 months	-	-	-

Abbreviations: EOT = End of Treatment, M = month, PD = progressive disease

Notes:

Predose/Before infusion: before the study drug infusion within the day

After 1 hour: 1 hour (±15 minutes) after the end of the study drug infusion

If a patient discontinues from the study drug at EOT 2, blood sampling for PK, Pharmacodynamics, immunoglobulin, immunogenicity and β-2 microglobulin will be conducted any time during the EOT 2 visit.

Efficacy: Tumour assessment during the Induction/Maintenance Study Period will be reviewed by central laboratory for reporting purpose.

If patient is terminated within 6 months from Day 1 of Cycle 1 of Induction Study Period, immunogenicity should be assessed at EOT2 (Month 3), EOT3 and the first Follow-up visit

APPENDIX 3: Table of CTCAE Terms and Grades

CTCAE Term	Laboratory Parameter	Level	Grade 1	Grade 2	Grade 3	Grade 4
Anemia	Hemoglobin	Low	<LLN - 10.0 g/dL; <LLN - 100 g/L	<10.0 - 8.0 g/dL; <100 - 80g/L	<8.0 g/dL; <80 g/L;	-
Alanine aminotransferase increased	Alanine Aminotransferase (ALT)	High	>ULN - 3.0 x ULN	>3.0 - 5.0 x ULN	>5.0 - 20.0 x ULN	>20.0 x ULN
Alkaline phosphatase increased	Alkaline phosphatase	High	>ULN - 2.5 x ULN	>2.5 - 5.0 x ULN	>5.0 - 20.0 x ULN	>20.0 x ULN
Aspartate aminotransferase increased	Aspartate Aminotransferase (AST)	High	>ULN - 3.0 x ULN	>3.0 - 5.0 x ULN	>5.0 - 20.0 x ULN	>20.0 x ULN
Blood bilirubin increased	Total Bilirubin	High	>ULN - 1.5 x ULN	>1.5 - 3.0 x ULN	>3.0 - 10.0 x ULN	>10.0 x ULN
Creatinine increased ¹	Creatinine	High	>1 - 1.5 x baseline; >ULN - 1.5 x ULN	>1.5 - 3.0 x baseline; >1.5 - 3.0 x ULN	>3.0 baseline; >3.0 - 6.0 x ULN	>6.0 x ULN
Hemoglobin increased ¹	Hemoglobin	High	Increase in >0 - 2 gm/dL above ULN or above baseline if baseline is above ULN	Increase in >2 - 4 gm/dL above ULN or above baseline if baseline is above ULN	Increase in >4 gm/dL above ULN or above baseline if baseline is above ULN	-
Hypercalcemia	Calcium	High	>ULN - 11.5 mg/dL; >ULN - 2.9 mmol/L	>11.5 - 12.5 mg/dL; >2.9 - 3.1 mmol/L	>12.5 - 13.5 mg/dL; >3.1 - 3.4 mmol/L	>13.5 mg/dL; >3.4 mmol/L
Hyperkalemia	Potassium	High	>ULN - 5.5 mmol/L	>5.5 - 6.0 mmol/L	>6.0 - 7.0 mmol/L	>7.0 mmol/L
Hypernatremia	Sodium	High	>ULN - 150 mmol/L	>150 - 155 mmol/L	>155 - 160 mmol/L;	>160 mmol/L

Hyperuricemia	Uric Acid	High	>ULN - 10 mg/dL (0.59 mmol/L) without physiologic consequences	-	>ULN - 10 mg/dL (0.59 mmol/L) with physiologic consequences	>10 mg/dL; >0.59 mmol/L
Hypoalbuminemia	Albumin	Low	<LLN - 3 g/dL; <LLN - 30 g/L	<3 - 2 g/dL; <30 - 20 g/L	<2 g/dL; <20 g/L	-
Hypocalcemia	Calcium	Low	<LLN - 8.0 mg/dL; <LLN - 2.0 mmol/L	<8.0 - 7.0 mg/dL; <2.0 - 1.75 mmol/L	<7.0 - 6.0 mg/dL; <1.75 - 1.5 mmol/L	<6.0 mg/dL; <1.5 mmol/L
Hypoglycemia	Glucose	Low	<LLN - 55 mg/dL; <LLN - 3.0 mmol/L	<55 - 40 mg/dL; <3.0 - 2.2 mmol/L	<40 - 30 mg/dL; <2.2 - 1.7 mmol/L	<30 mg/dL; <1.7 mmol/L
Hypokalemia	Potassium	Low	<LLN - 3.0 mmol/L	<LLN - 3.0 mmol/L	<3.0 - 2.5 mmol/L	<2.5 mmol/L
Hyponatremia	Sodium	Low	<LLN - 130 mmol/L	-	<130 - 120 mmol/L	<120 mmol/L
Neutrophil count decreased	Total Neutrophils	Low	<LLN - 1500/mm ³ ; <LLN - 1.5 x 10 ⁹ /L	<1500 - 1000/mm ³ ; <1.5 - 1.0 x 10 ⁹ /L	<1000 - 500/mm ³ ; <1.0 - 0.5 x 10 ⁹ /L	<500/mm ³ ; <0.5 x 10 ⁹ /L
Platelet count decreased	Platelet count	Low	<LLN - 75,000/mm ³ ; <LLN - 75.0 x 10 ⁹ /L	<75,000 - 50,000/mm ³ ; <75.0 - 50.0 x 10 ⁹ /L	<50,000 - 25,000/mm ³ ; <50.0 - 25.0 x 10 ⁹ /L	<25,000/mm ³ ; <25.0 x 10 ⁹ /L
White blood cell decreased	White Blood Cells	Low	<LLN - 3000/mm ³ ; <LLN - 3.0 x 10 ⁹ /L	<3000 - 2000/mm ³ ; <3.0 - 2.0 x 10 ⁹ /L	<2000 - 1000/mm ³ ; <2.0 - 1.0 x 10 ⁹ /L	<1000/mm ³ ; <1.0 x 10 ⁹ /L

Note: The LLN and ULN values will be the normal ranges as provided by the local laboratory at each relevant transfer.

1 The most severe grade is counted if the CTCAE grade is discrepant by multiple definitions

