5.5. Definition of Baseline

The baseline value will be considered to be the last non-missing value before the first administration of study drug. Post-baseline values will be considered to be all values collected after the first administration of study drug.

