13.2. Clinical Laboratory Evaluations

Clinical laboratory assessments of hematology, clinical chemistry and urinalysis will be performed at the local laboratory. Since reported units and normal ranges are various among sites, results will be converted to standard unit. Results of the assessment will be collected at the time points specified in the [APPENDIX 1](#).

Descriptive statistics for actual values and changes from baseline of each hematology or clinical chemistry parameter will be presented by visit for the Safety population.

All possible numeric parameters will be labeled and graded by CTCAE. Grades that require clinical input only will not be evaluated. Grades which are part numeric and part clinical input will be assigned based on the numeric portion only. CTCAE terms and ranges for applicable parameters are listed in [APPENDIX 3](#). The CTCAE grades for this analysis will be Grade 1 (Mild), Grade 2 (Moderate), Grade 3 (Severe) and Grade 4 (Life-threatening). The CTCAE Grade 5 (Death) will not be applied in this analysis since death cannot be determined from a numeric laboratory result. If the result for a patient does not satisfy any CTCAE grade, it will be classified as “No Grade”.

Results of unscheduled visits will be included for CTCAE grade. In summary, unscheduled visit and EOT visit results will be used in the related cycle. For example, C1D5 (Day 5 of Cycle 1 result will be summarized in Cycle 1; EOT1 result will be summarized in the last cycle of the Induction Study Period. In addition, C2D1 result should be summarized in Cycle 1 result because laboratory blood sample for C2D1 is taken before Cycle 2 dose administration. The same rule will be applied to subsequent cycles.

The number and percentage of patients who have a result for each grade will be summarized by laboratory category, CTCAE term, visit, grade and treatment group for the Safety population and Safety population – 2nd Maintenance Period subset. The summary will be presented in Overall and by each study period (up to MP1, MP2). Only the most severe case during unscheduled and scheduled visits will be included.

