The number and percentage of patients with CTCAE grade greater than or equal to 3 will be summarized by laboratory category, CTCAE term, grade and treatment group for the Safety population and Safety population – 2nd Maintenance Period subset. The summary will be presented in Overall and by each study period (up to MP1, MP2). Only the most severe case of the post-baseline during unscheduled and scheduled visits will be included.

The number and percentage of patients with CTCAE grade will be provided, by laboratory category, CTCAE term, grade and treatment group for the Safety population and Safety population – 2nd Maintenance Period subset, in the form of a shift table to detect changes from baseline. The summary will be presented in Overall and by each study period (up to MP1, MP2). Only the most severe case during unscheduled and scheduled visits will be included for the post-baseline result.

All hematology and clinical chemistry data will be listed by treatment group. Results of CTCAE will be presented by separate listing.

Result interpretation for all urinalysis parameters will be collected as {'Normal', 'Abnormal, not clinically significant' and 'Abnormal, clinically significant'}. The number and percentage of patients with urinalysis results will be provided, by parameter, visit and treatment group for the Safety population, in the form of a shift table to detect changes from baseline.

All urinalysis data will be listed by treatment group, visit and parameter.

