12. All screening laboratory safety assessments must be completed within 14 days before the first administration of the study drug. All laboratory safety assessments (haematology, clinical chemistry and urinalysis) must be completed within 3 days before Day 1 of each cycle during the Induction Study Period (except Cycle 1) and within 7 days before Day 1 of each cycle during the Maintenance Study Period. Testing will be performed at the local laboratory.
13. Clinical chemistry assessments will consist of sodium, potassium, blood urea nitrogen, creatinine, glucose, AST, ALT, alkaline phosphatase, total bilirubin, calcium, total protein, albumin, and uric acid.
14. Lactate dehydrogenase will be evaluated within 3 days before Day 1 of each cycle during the Induction Study Period (except Cycle 1) and within 7 days before Day 1 of each cycle during the Maintenance Study Period. Testing will be performed at the local laboratory. This should be performed at the time of response evaluation during the follow-up Study Period.
15. Urinalysis will consist of protein, blood, glucose, ketones, and bilirubin. If any of the dipstick analytes are 2+ or greater, a microscopic examination of urine will be performed with determinations of WBC, RBC, and bacteria counts.
16. Serum pregnancy tests in women of childbearing potential will be performed during the Screening Period (within 14 days before Day 1 of Cycle 1), at the EOT1 visit (within 3 days), the EOT2 visit (within 3 days), and the EOT3 visit (within 3 days). Serum pregnancy testing will be performed at the local laboratory. At Day 1 of each cycle during the Induction Study Period and the Maintenance Study Period, a urine pregnancy test will be performed. Urine pregnancy testing will be performed at the local laboratory.

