 26. Study drug (either CT-P10 or Rituxan), 375 mg/m² of BSA, will be administered on Day 1 of each cycle at 1 week intervals during Induction Study Period, and 8 weeks intervals during Maintenance Study Period. The first dose of study drug is to be administered at the same date with randomisation. Antipyretic (eg, paracetamol), antihistaminic (eg, H1 antihistamine), and glucocorticoid medications will be administered 30 minutes before each study drug infusion.
 27. 12-lead ECG will be obtained within 42 days before the first drug administration, EOT1, prior to Cycle 1 (Month 3; EOT2), Cycle 3 (Month 7), Cycle 6 (Month 13), Cycle 9 (Month 19) and the EOT3 visit during the Maintenance Study Period. Additional vital signs including systolic and diastolic blood pressure, heart rate, respiratory rate, and body temperature (before beginning the study drug infusion on Day 1 of each cycle [within 15 minutes before the beginning of the study drug infusion], at the end of study drug infusion [within 15 minutes after the end of the study drug infusion], and 60 minutes [±15 minutes] after the end of the study drug infusion) will be assessed to monitor for possible hypersensitivity reactions. In addition, hypersensitivity should be monitored by routine continuous clinical monitoring including ECG (3-lead or 12-lead) monitoring 60 minutes (±15 minutes) after the end of the study drug infusion. Emergency equipment, such as adrenaline, antihistamines, corticosteroids, and respiratory support (including inhalational therapy, oxygen, and artificial ventilator), must be available.
 28. Throughout the study, patients should be monitored for the clinical signs and symptoms of TB. Chest x-rays could also be used as a TB monitoring method. Patients with active TB will be excluded during the Screening Period. Chest x-rays for TB screening and clinical monitoring will be reviewed at the local level. Chest x-ray can be replaced by CT or proper image.
 29. All medications used during the study, as well as all medications taken from the signed date of the ICF until 30 days after the last dose of study drug administration or an EOT Visit, whichever is longer, will be recorded.

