Metabolism and nutrition disorders	Glucose tolerance impaired Hyperglycaemia Impaired fasting glucose	Hyperglycaemia
Immune system disorders	Drug hypersensitivity Hypersensitivity	Hypersensitivity
General disorders and administration site conditions	Catheter site pain Injection site haematoma Injection site pain Puncture site pain	Injection site reaction
Injury, poisoning and procedural complications	Chest injury Cartilage injury Craniocerebral injury Concussion Contusion Eye contusion Fall Injury Limb injury	Injury

	
Meniscus injury
 
Skin injury
 
Tendon rupture
 
Wound
 
Bone contusion
 
Back injury
 
Ear injury
 
Limb crushing injury
 
Muscle injury
 
Muscle rupture
 
Radiation skin injury
 
Skin abrasion
 
Laceration
	
Musculoskeletal and connective tissue disorders	
Intervertebral disc disorder
 
Intervertebral disc protrusion
	Intervertebral disc disorder
Infections and infestations	
Bacterial infection
 
Localised infection
 
Pulpitis dental
 
Skin infection
	Localised infection

	
Tooth infection
 
Tonsillitis bacterial
 
Staphylococcal infection
 
Eczema infected
 
Nail infection
 
Infected dermal cyst
	
Infections and infestations	
Bronchiolitis
 
Bronchitis
 
Lower respiratory tract infection
 
Lung infection
 
Respiratory tract infection
 
Respiratory tract infection viral
	Lower respiratory tract infection
Nervous system disorders	
Neuropathy peripheral
 
Peripheral sensory neuropathy
 
Toxic neuropathy
	Neuropathy peripheral
General disorders and administration site conditions	
Face oedema
 
Generalised oedema
 
Localised oedema
 
Oedema peripheral
	Oedema

	Peripheral swelling Swelling	
Infections and infestations	Otitis externa Otitis media Otitis media acute Otosalpingitis	Otitis
Infections and infestations	Pneumocystis jirovecii pneumonia Atypical mycobacterial pneumonia Pneumonia	Pneumonia
Skin and subcutaneous tissue disorders	Pruritus Pruritus generalised Pruritus allergic	Pruritus
Skin and subcutaneous tissue disorders	Rash Rash erythematous Rash generalised Rash macular Rash maculo-papular Rash pruritic	Rash
Infections and infestations	Rhinitis	Rhinitis

	Viral rhinitis	
Infections and infestations	Acute sinusitis Sinusitis Sinusitis bacterial	Sinusitis
Gastrointestinal disorders	Mouth ulceration Stomatitis Aphthous ulcer	Stomatitis

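### Creatinine Grade 1 starts just above a single baseline value and the worst draw is counted, so Grade 1 in the any-grade worst-case and shift tables is mostly noise; high glucose has no graded row

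*SAP*

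**What the plan says.** **Creatinine.** The row for increased creatinine in SAP Appendix 3 gives Grade 1 as ">1 - 1.5 x baseline; >ULN - 1.5 x ULN". Note 1, attached to this row, says: "The most severe grade is counted if the CTCAE grade is discrepant by multiple definitions". Meeting either definition is therefore enough.

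Section 5.5 fixes the comparator as one measurement: "The baseline value will be considered to be the last non-missing value before the first administration of study drug". For the shift table, Section 13.2 adds: "Only the most severe case during unscheduled and scheduled visits will be included for the post-baseline result". The worst-case rule also applies to the any-grade summary and to the Grade 3 or higher summary, each shown overall and by study period.

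**Glucose.** Section 13.2 states: "All possible numeric parameters will be labeled and graded by CTCAE". Section 13.2.2 lists glucose among the chemistry tests. Appendix 3 has a hypoglycemia row but no row for high glucose. Under Section 13.2, a result that meets no grade is classed as No Grade.

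**The concern.** A patient whose creatinine fluctuates around a constant level will sooner or later have a value above the single baseline draw. Under these rules one such value in any later sample makes the patient Grade 1, even well inside the normal range. The baseline value cannot exceed itself, so it can be graded only against ULN. A move from No Grade to Grade 1 is thus built into the shift table.

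Creatinine is the only row in Appendix 3 that works this way. The liver tests start at ULN, and the row for increased haemoglobin refers to baseline only when baseline is already above ULN.

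Comparing overall safety is a stated secondary objective (SAP Section 3.2). If most patients in both arms are Grade 1 by chance, a modest number of real low-grade rises in one arm will hardly move the count.

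For glucose, the missing row leaves Appendix 3 at odds with the general statement in Section 13.2 and merges high with normal values in the graded tables.

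**Working it through.** The documents give no expected rate of increased creatinine, so there is no figure of the plan's own to reproduce.

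**Step 1: number of draws (SAP Appendix 1, clinical chemistry row and footnote 12).** No chemistry draw is planned at Induction Cycle 1, so baseline is normally the screening draw. Post-baseline scheduled draws are:
- To Maintenance Cycle 3: Induction Cycles 2, 3 and 4, EOT1, and predose Maintenance Cycles 1, 2 and 3 = 7.
- To the end of MP1: add predose Maintenance Cycles 4 to 7 = 11. Section 13.2 assigns a predose result to the preceding cycle, so the Cycle 7 draw belongs to Cycle 6.
- To EOT3 through MP2: 4 in induction + 12 in maintenance + EOT3 = 17.

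Unscheduled draws add to these counts.

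**Step 2: exact result.** Assume no true change and continuous, exchangeable values. Baseline is then equally likely to hold any rank among the k + 1 values, so P(at least one later value above baseline) = k/(k + 1).
- k = 7: 7/8 = 87.5%
- k = 11: 11/12 = 91.7%
- k = 17: 17/18 = 94.4%

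**Step 3: simulation for ties and serial correlation.** Each setting used 400,000 patients. The inputs are assumptions, not document figures: median set point 75 umol/L, between-patient CV 20%, within-patient CV 3-12%. Each range below runs over the within-patient CV.

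| Setting | 7 draws | 11 draws | 17 draws |
|---|---|---|---|
| Rounded to 1 umol/L | 83.0-86.7% | 88.2-91.0% | 91.6-94.0% |
| Same, lag-1 correlation 0.5 | 79.6-84.1% | about 86-89% | 90.1-92.7% |
| All laboratories report to 0.1 mg/dL | 37-77% | 42-83% | 47-88% |
| Above 1.5 x baseline, CV 3-8% | 0-0.1% | 0-0.2% | 0-0.2% |
| Above 1.5 x baseline, CV 12% | 4.3% | 6.0% | 8.0% |

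If all 87 planned patients in an arm had seven draws, the first row gives 0.830 x 87 = 72 to 0.867 x 87 = 75 patients at Grade 1 or higher by chance. At a single visit the chance rate is about 44-50% with fine reporting.

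**Step 4: sensitivity to a real shift.** At CV 5% with 1 umol/L rounding and 7 draws, the rate is 85.0% with no shift, 56% if every patient truly falls by 5%, and 97% if every patient truly rises by 5%. With 17 draws the rates are 93.0%, 71% and 99%.

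**Step 5: what noise hides.** Suppose 5 patients in one arm, with normal baselines, truly rise into the band from ULN to 1.5 x ULN. At an 85% background, 5 x 0.85 = 4.25 of them would be Grade 1 anyway, so the count moves by about 0.75. At 94% it moves by 5 x 0.06 = 0.3. Graded against ULN alone, the same patients add 5.

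**Step 6: glucose.** Sodium, potassium and calcium each have a high and a low row in Appendix 3. Glucose has only the low row, and no reason is given.

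**The case against.** Several points on the other side stand.

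- **Other outputs remain.** Section 13.2 also plans by-visit descriptive statistics of actual values and changes for every chemistry parameter, plus full listings. These show small creatinine shifts and high glucose. Hyperglycaemia reported as an adverse event receives a CTCAE intensity, and Appendix 5 groups "Glucose tolerance impaired Hyperglycaemia Impaired fasting glucose" under one term. A reader might infer that the laboratory tables cannot show high glucose at all; that is wrong.
- **Higher grades stay usable.** Grade 2 is rarely crossed by chance unless within-patient variation is large, and the Grade 3 or higher table is essentially untouched. Grades shown by visit are noisy but not saturated.
- **No bias between arms.** Inflation is the same in both, and the SAP plans no test or margin for laboratory grades. Nor is the creatinine table blind to every difference: Step 4 shows that a uniform shift would still move it.
- **The percentages are modelled.** Section 13.2 says local units vary and gives no reporting precision. The 17-draw figure needs treatment through MP2, which is optional. A patient with four draws has a chance rate of 4/5 = 80%.
- **Glucocorticoid premedication is a weak argument for the glucose row.** Appendix 1 says "glucocorticoid medications will be administered 30 minutes before each study drug infusion", but scheduled chemistry is drawn before the infusion, within 3 days of Day 1 in induction and within 7 days in maintenance. It normally precedes that cycle's premedication and follows the previous one by days or weeks.
- **Appendix 3 is described as covering applicable parameters,** and many of its rows run in one direction only. That leaves room for a deliberate omission, for example because fasting status is not controlled, but no reason is stated.

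Following the declared grading scale for creatinine is also defensible. What remains is that applying it mechanically to every draw and keeping the maximum makes Grade 1 uninformative in two sets of tables.

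**Conclusion.** The point holds for the any-grade worst-case summaries and the shift table. With no true change and fine reporting, about 83-94% of patients would be at least Grade 1 for creatinine by chance. The range is about 80-93% with lag-1 correlation 0.5, and 37-88% if all laboratories report only to 0.1 mg/dL. The upper ends apply only to patients followed through MP2. These ranges rest on the assumed within-patient CV of 3-12% and should not be read as an observed or document-based rate. The consequence is lost resolution at Grade 1 in both arms alike. It does not favour either product and does not touch the primary endpoint.

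On glucose, Section 13.2 and Appendix 3 do not agree as written. The effect is confined to the graded laboratory tables, where high values are counted with normal ones.

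**What to change.** 1. Keep the declared creatinine grades, but in the worst-grade and shift tables present the ULN-based and baseline-based grades as separate rows. This departs from no definition and gives a readable low-grade comparison. Restricting Grade 1 to the ULN criterion would also remove the noise, but it departs from the declared scale and drops rises within the normal range from Grade 1, so it is the less attractive choice.
2. Add a high-glucose row to Appendix 3 or, if fasting status is not recorded, a shift table against the local ULN, which the laboratories already supply. If the row is left out on purpose, state the reason so that Appendix 3 and Section 13.2 agree.

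Both changes use data already collected. The cost is a few extra table rows and the programming for them.
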